2.3 PARTICIPANT REGISTRATION AND STATUS UPDATE PROCEDURES

Registration and status updates (e.g. when a participant is taken off protocol therapy and when a participant is taken off-study) will take place per CCR SOP ADCR-2, CCR Participant Registration & Status Updates found here.

2.3.1 Treatment assignment and randomization procedures:

Cohorts

Number Name		Description					
1	Patients	Patients with vulvar HSIL					

Arms

Number	Name	Description					
1	Arm 1	1×10^{11} E7 TCR T cells will be administered intravenously over 20 to 30 minutes on day 0.					

Arm Assignment

Patients in Cohorts 1 will be directly assigned to Arm 1.

2.4 **BASELINE PROCEDURES**

[figure not shown]
- 2.4.1 Within 14 days prior to starting therapy (unless otherwise indicated):
 - a. Complete history and physical examination
 - a. Chem 20 equivalent: (Sodium (Na), Potassium (K), Chloride (Cl), Total CO2 (Bicarbonate), Creatinine, Glucose, Urea nitrogen (BUN), Albumin, Calcium total, Magnesium total (Mg), Inorganic Phosphorus, Alkaline Phosphatase, ALT/GPT, AST/GOT, Total Bilirubin, Direct Bilirubin, LDH, Total Protein, Total CK, Uric Acid).
 - b. TSH
 - c. CBC with differential and TBNK
 - d. PT/PTT
 - e. Beta-HCG pregnancy test (serum or urine) on all women of child-bearing potential
 - f. ECOG performance status assessmentBaseline photographs and biopsies of HSIL lesions to be performed under local anesthetic in the clinic within 8 weeks prior to therapy. Patients will be required to sign a separate consent for all biopsies conducted during the study. Refer to Section 5.4 for guidelines for handling specimens. Peripheral blood lymphocytes (PBLs), plasma, and serum collected at time of baseline biopsy. As noted in 5.1.3, Biopsies will not be performed if they are not technically feasible, if they will interfere with response assessment, or if a patient declines consent. Replication Competent Retrovirus (RCR) testing.Leukapheresis as described in section 3.1.2.

3 STUDY IMPLEMENTATION

3.1 STUDY DESIGN

This is a single arm phase II clinical trial using a Simon minimax two-stage design. Twelve patients will be treated initially, which will be expanded to sixteen patients if one or more patient(s) have a complete response in the initial 12 patients.

3.1.1 Protocol Schema

3.1.2 Leukapheresis

The patient will undergo a 10-15 liter leukapheresis (generally, 12 liters will be processed to target yield of 6-10 $\times 10^9$ lymphocytes) in the Department of Transfusion Medicine (DTM) Dowling Apheresis Clinic according to DTM standard operating procedures. The procedure requires dual venous access, and takes approximately 3-4 hours to complete. A central line will be placed if peripheral venous access is not sufficient. The leukapheresis collection will be obtained at least 21 days prior to the cell infusion. Leukapheresis material that is not required for clinical use will be retained and cryopreserved in 10 vials at 100×10^6 cells per vial with remaining cells stored at 300x10⁶ cells per vial for research and banked on this study and protocol 16-C-0061 (ETIB Tissue Procurement Protocol) if the subject coenrolled on that study. Patients previously treated on protocol 17-C-0116 will not undergo leukapheresis to generate a cell product.

3.1.3 E7 TCR T cell preparation

After cells are obtained by apheresis, further cell processing to generate E7 TCR cells will occur in the DTM according to standard operating procedures and the E7 TCR investigational new drug application. E7 TCR cells can be produced in approximately 21 to 27 days. Cell products may be cryopreserved during production to accommodate patient treatment schedules. Either freshlycollected cells or cryopreserved cells can be used to initiate the cell-preparation process. Peripheral blood mononuclear cells (PBMC) will be isolated. Sufficient cells for three complete cell productions (2-3 vials at 3-4.5 x 10^9 cells/vial) will be retained in the DTM; the remaining cells will first be frozen in 10 vials at 100 x 10^6 cells per vial with excess frozen at 300 x 10^6 cells/vial. Cells will be frozen in the DTM and then transferred to ETIB the following day. The ETIB preclinical core contact is [name] [contact]).

Before infusion, the percentage of T cells expressing the E7 TCR will be determined by flow cytometry. Successful TCR gene transfer will be defined as greater than 20% TCR positive cells. In addition to flow cytometry, further testing of the cells will take place prior to infusion to evaluate for microbial contamination, replication-competent retroviruses, and viability. Details of this testing can be found in the appropriate DTM SOPs. When a patient is no longer eligible for retreatment (see section 3.4) on this protocol due to meeting any of the off-study criteria listed in Section 3.6.2, any remaining pretreatment PBMC collected on this protocol and cryopreserved as described in Section 3.1.2 will be transferred from the Department of Transfusion Medicine to the Principal Investigator of this protocol 16-C-0061 (ETIB Tissue Procurement Protocol) if the subject coenrolled on that study. Cell products for patients treated on protocol 17-C-0116 will be generated from previously collected PBMC products retained in the DTM.

3.1.4 Treatment Phase

E7 TCR T cells will be infused while the patient is admitted to the hospital on treatment day 0. A central line catheter may be placed for cell infusion. Patients will be observed overnight as inpatients following administration of cells, and will not be discharged until cleared by the treating physician. Patients will receive one course of treatment unless eligible for retreatement as discussed in section **3.4**.

3.1.5 Safety Protocol Stopping Rules

The study will be halted (immediately stop accrual and treatment) if any of the following safety conditions are met and we will promptly investigate and submit an amendment to the IRB and FDA if necessary:

- 1. If one or more deaths (other than death related to progressive disease) occurs within 30 days of E7 TCR T cells.
- 2. If 2 of the first 6 patients or the fraction of patients > 33% after the initial 6 patients develop grade 4 or greater adverse events (except lymphocyte count increased) possibly related to E7 TCR Tcells.

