3.4 POTENTIAL REPEAT TREATMENT

Patients may be retreated if an E7 T cell product can be generated from cells collected prior to any T cell gene therapy treatment. Patients eligible for retreatment include those who had partial or complete response to E7 TCR T cell therapy that subsequently progress. Patients must meet the original eligibility criteria to be considered for retreatment. Research assessments will be performed at the same time intervals used for initial treatment. Patients who develop grade 3 or 4 toxicity due to cell infusion will not be retreated. A maximum of 1 retreatment course may occur. The second treatment will not begin until at least 12 weeks after initial T cell therapy but must be within 5 years from the date of progressive disease.

Note: Response data for all treatments will be captured in the database however only the response data from the first treatment with E7 TCR T cells will be used in determination of response.

3.5 **ON-STUDY EVALUATIONS**

Please see the study calendar in Section 3.3 for details regarding on-study evaluations.

3.5.1 Long-term Follow-Up:

Long-term follow-up of patients receiving gene transfer is required by the FDA and must continue even after the patient comes off the study. Long-term follow-up will be done under a different long-term gene therapy follow-up protocol (20C0051).

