7.3 NCI CLINICAL DIRECTOR REPORTING

Problems expeditiously reported to the OHSRP in iRIS will also be reported to the NCI Clinical Director. A separate submission is not necessary as reports in iRIS will be available to the Clinical Director.

In addition to those reports, all deaths that occur within 30 days after receiving a research intervention **s**hould be reported via email to the Clinical Director unless they are due to progressive disease.

To report these deaths, please send an email describing the circumstances of the death to [name] at [contact] within one business day of learning of the death.

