10.1.3 Sample Size Determination

This trial will be conducted using a Simon minimax two-stage phase II trial design(25) to rule out an unacceptably low CR rate of 5% (p0=0.05) in favor of an improved complete response rate of 25% (p1=0.25). With alpha=0.10 (probability of accepting a poor treatment=0.10) and beta = 0.20 (probability of rejecting a good treatment=0.20), the first stage will enroll 12 evaluable patients, and if 0 of the 12 have a complete response, then no further patients will be accrued. If 1 or more of the first 12 patients have a complete response, then accrual would continue until a total of 16 evaluable patients have been treated. As it may take up to several months to determine if a patient has experienced a complete response, a temporary pause in the accrual may be necessary to ensure that enrollment to the second stage is warranted. If there are 1-2 patients with a complete response out of 16 patients, this would be an uninterestingly low

complete response rate. If there were 3 or more of 16 (18.75%) who experienced a complete response, this would be sufficiently interesting to warrant further study in later trials. Under the null hypothesis (5% complete response rate), the probability of early termination is 54.0%. In patients that undergo retreatment, only the first response to E7 TCR T cell treatment will be used in the calculation of complete response rate.

Since patients will be screened on this protocol, to allow for patients who enroll but are not evaluable for the primary endpoint, as well as screen failures, up to 200 patients total may be enrolled. It is expected that up to 10-12 treated patients can be enrolled within one year; thus, up to 18 months may be required to accrue 16 evaluable patients. Up to 16 patients may be treated in order to allow for a small number of inevaluable, treated patients.

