10.2.4 Safety Analyses

If two of the first six patients develop any grade 4 event related to E7 TCR T cells or grade 3 events (except lymphocyte count increased) that does not resolve to a grade 2 or less in 48 hours or the fraction of participants with these events is greater than or equal to 33% after the initial 6 patients, then no further patients will be accrued as soon as this has been determined. Accrual may resume after appropriate treatment revision is described in approved amendment. All treatment courses with E7 TCR T cells will be considered in this analysis.

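### A death possibly related to E7 TCR T cells more than 30 days after the most recent infusion does not by itself trigger the automatic halt in section 3.1.5

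*Combined protocol and SAP*

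**What the plan says.** Section 3.1.5 of the combined protocol and SAP has two conditions, either of which halts both accrual and treatment at once.

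- Rule 1 is a single-death trigger with a time limit and no attribution requirement: "If one or more deaths (other than death related to progressive disease) occurs within 30 days of E7 TCR T cells". A death within 30 days of a retreatment infusion is reasonably read as covered too.
- Rule 2 has no time limit but needs several patients. It is met by 2 of the first 6 patients, or when "the fraction of patients > 33% after the initial 6 patients develop grade 4 or greater adverse events" that are possibly related to the cells (an increased lymphocyte count is excepted).

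Section 10.2.4 gives a second rule of the same shape. It opens "If two of the first six patients develop any grade 4 event related to E7 TCR T cells or grade 3 events" (the latter if not down to grade 2 or less in 48 hours). Afterwards it applies when "the fraction of participants with these events is greater than or equal to 33% after the initial 6 patients". Its consequence is narrower: "then no further patients will be accrued as soon as this has been determined". It does not name grade 5 and has no trigger for a single death.

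Infusions can still be going on well after any one patient's day 30. Section 10.1.3 allows up to 18 months to accrue 16 evaluable patients. Section 3.4 allows one retreatment: "The second treatment will not begin until at least 12 weeks after initial T cell therapy", and it may be given up to 5 years from progression.

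**The concern.** As written, an unrelated death on day 29 must stop the trial, while a death attributed to the product on day 31 need not. Rule 1 shows that one death is thought serious enough to stop on. The available text does not say why that should lapse at day 30 when the cells are suspected as the cause.

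The disease is premalignant and the listed alternative is surgery (sections 1.2 and 12.5). One product-related death is therefore reason to hold the next infusion until it has been investigated. The plan itself expects delayed risk to be watched: it tests for replication-competent retrovirus at about 3, 6 and 12 months, records related events beyond 28 days, and requires enrolment in long-term follow-up. At stake is whether the next patient, new or retreated, can be infused before that investigation without breaching the stopping rules.

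**Working it through.** **Plan's own figure.** The plan states no operating characteristic for either safety rule, so there is none to reproduce. The one it does state, 54.0% early termination, belongs to the efficacy design (0.95^12 = 0.5404) and plays no part here.

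**Inputs.** From 3.1.5: 2 of the first 6, then a fraction above 33%. From 10.2.4: at least 33%. From 10.1.3: up to 16 treated patients.

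**Step 1, where the death falls.** Later than 30 days after the most recent infusion, rule 1 does not apply. Rule 2 does, because a fatal event is above grade 4 and no time limit is set. The death counts as one patient, or adds nothing if that patient was already counted for an earlier grade 4 event.

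**Step 2, patients needed.** For n above 6, find the smallest whole number k with k/n > 0.33, taking n as all patients treated so far. After one counted death, k − 1 further patients are needed.

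| Treated, n | k needed (limit 0.33) | Further patients, k − 1 | k needed if 33% means one third | Share of one patient |
|---|---|---|---|---|
| First 6 | 2 | 1 | 2 | count rule |
| 7–8 | 3 | 2 | 3 | 14.3%–12.5% |
| 9 | 3 | 2 | 4 | 11.1% |
| 10–11 | 4 | 3 | 4 | 10.0%–9.1% |
| 12 | 4 | 3 | 5 | 8.3% |
| 13–14 | 5 | 4 | 5 | 7.7%–7.1% |
| 15 | 5 | 4 | 6 | 6.7% |
| 16 | 6 | 5 | 6 | 6.25% |

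The fourth column differs at n = 9, 12 and 15 because 3/9, 4/12 and 5/15 equal one third exactly and so do not exceed it. The further patients may be newly treated, or already treated and having a late event.

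**Step 3, does 10.2.4 close the gap?** Its at-least-33% limit gives the second column of the table whether 33% is taken as 0.33 or as one third. Unresolved grade 3 events also count there, so earlier ones would lower the number still needed. If grade 5 is not counted because it is not named, the death adds nothing. Either way, one death alone does not reach 2 of 6 or 33%.

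**Step 4, exposure.** Until a limit is met, up to 16 − n first infusions, plus any retreatments, could go ahead without a required halt. Around n = 12 accrual may already be on hold for the stage 1 assessment ("a temporary pause in the accrual may be necessary to ensure that enrollment to the second stage is warranted").

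No probability is given, because the documents give no rate of late related deaths.

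**The case against.** This is a design choice rather than an error. The plan combines an all-cause 30-day death halt with a related-toxicity rule that has no time limit and already counts late deaths. Any fixed window produces a contrast at its edge, and this one matches the Clinical Director report in section 7.3, which covers "all deaths that occur within 30 days after receiving a research intervention" unless due to progressive disease.

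The event is also unlikely: the end of section 1.2 reports no long-term toxicity with retrovirally transduced mature T cells since 1989. Nor would a late death go unnoticed. Serious events are reported within 24 hours (8.3), and unexpected fatal events associated with the cells go to the IBC within 7 days (7.4.1). The team meets weekly during active treatment (7.5.1), and infusions may be delayed as medically indicated (3.2.1). At 10–12 treated patients a year, first infusions come on average every 365/12 = 30 to 365/10 = 37 days, so these steps would usually come first once the death is known. Retreatment is limited to responders who later progress. Surgery, finally, has already failed these patients or would have results they cannot accept.

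All of this stands, and it lowers the urgency. It does not supply the missing rule. Those routes inform people or permit a pause; none of them, as stated in this protocol, requires one.

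Two stronger readings should be resisted. A reader might infer that rule 2 can never be met by one patient. That fails if the 33% is taken only over patients treated after the sixth, where one event gives 1/1, 1/2 or 1/3, each above 0.33. It is not the ordinary reading, and 10.2.4 words its limit as a running fraction of participants, but 3.1.5 does not rule it out. A reader might also infer that nothing anywhere would compel a halt. Sections 7.2 and 5.3 rely on NIH Policies 801 and 802 and on protocol 20C0051, whose contents are not in the documents, so the claim extends only to this protocol.

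**Conclusion.** The gap is real on the ordinary cumulative reading of rule 2. A possibly related death more than 30 days after the most recent infusion is one patient toward a limit of 2 of the first 6, then 3 to 6 as n goes from 7 to 16. It does not by itself halt the trial under 3.1.5 or stop accrual under 10.2.4, and this protocol states no other mandatory halt for it.

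A reader might go further and infer that dosing would in practice continue after such a death. The documents do not support that: 16 − n is a ceiling on what is permitted, not a forecast, and a discretionary pause is probable.

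The conclusion rests on what the rules require, not on how often the event occurs. Parts of the background in section 1.2 were not available. The point is a cheap improvement that should be made, and it does not touch the efficacy design.

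**What to change.** Keep the 30-day all-cause trigger. Add one sentence to 3.1.5, with a cross-reference in 10.2.4: any death assessed as at least possibly related to E7 TCR T cells (recorded as related under 8.1.5), at any time after any infusion while accrual or treatment is ongoing, also halts accrual and treatment pending investigation, whatever the rule 2 percentage.

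The cost is a short amendment and an occasional temporary halt for a late death later judged unrelated. Sample size and the two-stage design are unchanged.

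The new rule's reach depends on deaths being reported. Section 6.1 keeps recording related events after day 28, the calendar includes an annual patient status update, and death is an off-study criterion. But non-responders are referred to standard care at month 3, and the items listed for the annual contact are procedures, treatments and cancers, not deaths. Deaths after clinic follow-up would act on the rule only as they become known, for example through 20C0051.

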7.5 NIH REQUIRED DATA AND SAFETY MONITORING PLAN

7.5.1 Principal Investigator/Research Team

The clinical research team will meet on a weekly basis when patients are being actively treated on the trial to discuss each patient.

All data will be collected in a timely manner and reviewed by the principal investigator or a lead associate investigator. Events meeting requirements for expediated reporting as described in section 7.2.1 will be submitted within the appropriate timelines.

The principal investigator will review adverse event and response data on each patient to ensure safety and data accuracy. The principal investigator will personally conduct or supervise the investigation and provide appropriate delegation of responsibilities to other members of the research staff.

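### Sections 3.1.5 and 10.2.4 give two current toxicity stopping rules that do not cite each other and differ in qualifying event, threshold, attribution, action and restart condition

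*Combined protocol and SAP*

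**What the plan says.** Section 3.1.5, the only section headed as stopping rules, opens: "The study will be halted (immediately stop accrual and treatment) if any of the following safety conditions are met". One condition is any death within 30 days of the cells that is not due to progression. The other is met when two of the first six patients, or more than 33% after that, "develop grade 4 or greater adverse events (except lymphocyte count increased) possibly related to E7 TCR Tcells". The team then investigates and will "submit an amendment to the IRB and FDA if necessary".

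Section 10.2.4, in the statistics chapter, is triggered when two of the first six patients, or at least 33% after that, have a grade 4 event related to the cells or "grade 3 events (except lymphocyte count increased) that does not resolve to a grade 2 or less in 48 hours". The consequence is "then no further patients will be accrued as soon as this has been determined". On restart it says "Accrual may resume after appropriate treatment revision is described in approved amendment", and on scope "All treatment courses with E7 TCR T cells will be considered in this analysis". Section 3.1.5 does not say which courses count.

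Both are current text. Nothing in the protocol says which governs, or that a stop applies when either is met.

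**The concern.** The rule limits how many patients with a premalignant condition receive a gene-modified cell product before someone must stop and look. Staff will naturally turn to the section headed as stopping rules. That section ignores grade 3 events altogether, however long they last, whereas the statistics chapter treats prolonged grade 3 toxicity as a reason to stop. A team using 3.1.5 alone would go on enrolling and infusing after events that 10.2.4 says stop accrual.

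A team using 10.2.4 alone would stop enrolment. It would find no explicit instruction on patients already enrolled and awaiting a product, or on those due for the retreatment allowed in 3.4.

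**Working it through.** **The two rules side by side**

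| | 3.1.5 | 10.2.4 |
|---|---|---|
| (a) Event | grade 4 or greater | grade 4, plus grade 3 still above grade 2 at 48 hours |
| (b) Threshold after six patients | > 33% | >= 33% |
| (c) Attribution | possibly related | related |
| (d) Action | accrual and treatment stop | accrual stops; treatment not mentioned |
| (e) Restart | amendment if necessary | approved amendment required |

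On (a), if two of the first six patients have only prolonged grade 3 events, 10.2.4 trips and 3.1.5 does not. In the extreme, all 16 patients could have such events without tripping the 3.1.5 toxicity condition.

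On (c), section 8.1.5 allows only two categories, related and not related, so the 3.1.5 term is not on the scale in use. In 10.2.4 the word *related* follows grade 4, and it is unclear whether it also governs grade 3. The lymphocyte exception there follows grade 3, and it is equally unclear whether it covers grade 4.

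**Does (b) matter?** The smallest number of affected patients that trips each rule after patient six is:

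| Patients treated | 33% read as 0.33, both rules | One third, > | One third, >= |
|---|---|---|---|
| 7-8 | 3 | 3 | 3 |
| 9 | 3 | 4 | 3 |
| 10-11 | 4 | 4 | 4 |
| 12 | 4 | 5 | 4 |
| 13-14 | 5 | 5 | 5 |
| 15 | 5 | 6 | 5 |
| 16 | 6 | 6 | 6 |

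The thresholds differ only if 33% means one third, and then only at 9, 12 and 15 patients.

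**Size of (a).** The plan gives no operating characteristics for either toxicity rule, so there is no figure to reproduce. The inputs from the plan are the two-in-six boundary, the 33% fraction and the maximum of 16 evaluable patients (10.1.3). The toxicity rates are assumptions: p4 is the share of patients with a grade 4 event, and p3 the share with only a prolonged grade 3 event. Patients are taken as independent and checked one at a time, 33% is read as 0.33, grade 5 is not modelled separately, and attribution is taken as the same under both rules.

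Under 3.1.5 the event probability is p = p4; under 10.2.4 it is p = p4 + p3. By patient six:

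P(stop) = 1 - (1-p)^6 - 6p(1-p)^5

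- p = 0.05: 1 - 0.7351 - 0.2321 = 0.0328
- p = 0.10: 1 - 0.5314 - 0.3543 = 0.1143

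Beyond six, let f_n(k) be the probability of k affected patients among n with no stop so far. Then f_n(k) = f_{n-1}(k)(1-p) + f_{n-1}(k-1)p, and any mass at or above the boundary for n is moved to *stopped*. By patient 16 this gives 0.0349 at p = 0.05 and 0.1291 at p = 0.10.

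Every patient counted by 3.1.5 is counted by 10.2.4 in this model, so the chance that 10.2.4 trips and 3.1.5 does not is the difference: 0.1291 - 0.0349 = 0.0942.

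| By patient 16, p4 = 5% | p3 = 1% | 2% | 5% | 10% | 20% |
|---|---|---|---|---|---|
| Stop under 3.1.5 | 3.5% | 3.5% | 3.5% | 3.5% | 3.5% |
| Stop under 10.2.4 | 5.0% | 6.6% | 12.9% | 26.5% | 57.5% |
| Only 10.2.4 trips | 1.5% | 3.1% | 9.4% | 23.0% | 54.0% |

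Over the same p3 range, the last row runs from 0.7% to 47.8% at p4 = 2% and from 2.4% to 58.2% at p4 = 10%. Reading 33% as one third moves the central figure only from 0.0942 to 0.0955.

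**Size of (d).** Production takes 21 to 27 days (3.1.3), and 10 to 12 treated patients a year are expected (10.1.3). The mean number of patients with a product in manufacture is 10 x 21/365 = 0.58 to 12 x 27/365 = 0.89. This assumes steady accrual and infusion as soon as the product is ready. Section 3.1.3 allows cryopreservation during production, which would raise the number waiting.

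**The case against.** The strongest reply is that nothing conflicts. Section 3.1.5 lists conditions that stop the trial and does not say they are the only ones; 10.2.4 adds another. No event makes one section forbid what the other requires, and a compliant team follows both. This stands. A reader might infer that the rules contradict each other, or that the percentages above are chances of a missed stop. The documents support neither: the percentages are chances that the two rules give different answers, and under joint compliance no stop is missed.

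Second, the events would be seen. Section 7.5.1 states: "The clinical research team will meet on a weekly basis when patients are being actively treated on the trial to discuss each patient". Serious events reach the sponsor within 24 hours of awareness (8.3), and section 3.4 bars retreatment after grade 3 or 4 toxicity due to the cell infusion. This also stands, but seeing an event does not settle which rule applies to it. Safety Monitoring Committee review is roughly annual (7.5.2), so day-to-day application rests with the study team.

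Third, the treatment gap may be narrower than the wording suggests. Section 10.1.3 speaks of accrual continuing until patients have been treated, and 10.2.4 makes resumption depend on a revised treatment. Infusing waiting patients with the unrevised regimen would sit badly with that. A reader might infer that 10.2.4 permits those infusions. It does not say so; it leaves the matter open.

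Fourth, the rates are invented. That is correct, and no row of the table is favoured by the text. Sections 12.3, 12.5 and 12.6 refer to known risks from earlier E7 TCR experience, and part of the background in 1.2 was not in the text reviewed. The absence of rates is therefore a statement about the reviewed text only.

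**Conclusion.** The concern holds as a failure to reconcile two live safety rules, and it should be fixed. The five differences follow from the text without any assumption. The most important is that prolonged grade 3 events count in one section and not in the other; next is whether infusions stop. The > versus >= difference is small.

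The practical size cannot be fixed from the reviewed text. The 3.5% versus 12.9% comparison illustrates one assumed pair of rates, under independence, identical attribution and 33% read as 0.33. If 10.2.4 was meant to count grade 3 events regardless of attribution, the gap would be at least as large for the same related-event rates.

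A reader might also infer that the efficacy result is at risk. It is not: the complete-response definition and its analysis use neither rule.

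**What to change.** Put one rule in 3.1.5 and have 10.2.4 cite it:

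- **Trigger:** two of the first six patients, or one third or more thereafter, with a grade 4 or greater event, or a grade 3 event that has not fallen to grade 2 or below within 48 hours. Lymphocyte count increased is excepted throughout.
- **Attribution:** assessed as related under 8.1.5, that is, a reasonable possibility. If the sponsor meant grade 3 events to count whatever their cause, say so explicitly.
- **Counting:** all courses, each patient once.
- **Action:** halt accrual and all infusions, including patients awaiting a product and retreatment.
- **Restart:** only after an approved amendment.
- **Keep** the separate 30-day death rule unchanged.

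The cost is protocol wording, with no extra patients, visits or data. The downside is a somewhat higher chance of a temporary pause than under 3.1.5 alone: in the illustration, 12.9% instead of 3.5% by patient 16. If the team already applies both rules together, the added grade 3 trigger brings essentially no further accrual stops.
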